7.5. Preparation/Handling/Storage/Accountability

The investigator or designee must confirm appropriate temperature conditions have been maintained, as communicated by the sponsor, during transit for all investigational products received and any discrepancies are reported and resolved before use of the study treatment.

Only participants enrolled in the study may receive investigational product or study materials, and only authorized site staff may supply or administer investigational products. All investigational products should be stored in an environmentally controlled and monitored (manual or automated) area in accordance with the labeled storage conditions with access limited to the investigator and authorized site staff.

The investigator, institution, or the head of the medical institution (where applicable) is responsible for study treatment accountability, reconciliation, and record maintenance (such as receipt, reconciliation, and final disposition records).

7.6. Treatment Compliance

The investigational products will be administered at the clinical site, and documentation of treatment administration will occur at the site.

7.7. Concomitant Therapy

Subjects on stable concomitant medications at the time of study entry should continue their regular, unchanged dose throughout the study.

In general, concomitants medication should be avoided; however, acetaminophen (1 g, maximum 4 g/24 hours) may be administered at the discretion of the investigator for treatment of headache, etc. If the need for concomitant medication (other than acetaminophen) arises, inclusion or continuation of the subject may be at the discretion of the investigator after consultation with a Lilly CP or CRP. Any medication used during the study must be documented.

Vitamin/mineral supplements are not allowed during the study.

Drugs that are known strong inducers or inhibitors of CYP3A or OATPs and known substrates of OATPs or BCRP are specifically excluded. For more information, refer to [Appendix 6](#).

7.8. Treatment after the End of the Study

Not applicable.

8. Discontinuation Criteria

Subjects discontinuing from the treatment prematurely for any reason should complete AE and other follow-up procedures per Section 2 of this protocol.

Subjects discontinuing from the treatment or from the study prematurely for any reason should complete AE and other follow-up procedures per Section 2 of this protocol.

8.1. Discontinuation from Study Treatment

In Part B, discontinuation of the investigational product for abnormal liver test results **should be considered** by the investigator when a subject meets 1 of the following conditions, after consultation with the Lilly-designated medical monitor:

- ALT or AST >8X ULN
- ALT or AST >5X ULN sustained for more than 2 weeks or
- ALT or AST >3X ULN and TBL >2X ULN or international normalized ratio >1.5 or
- ALT or AST >3X ULN with the appearance of fatigue, nausea, vomiting, right upper-quadrant pain or tenderness, fever, rash, and/or eosinophilia (>5%)
- ALP >3X ULN
- ALP >2.5X ULN and TBL >2X ULN
- ALP >2.5 ULN with the appearance of fatigue, nausea, vomiting, right quadrant pain or tenderness, fever, rash, and/or eosinophilia (>5%)
- creatine kinase >5x ULN.

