2.2. Part B (Cohorts 1 and 3; Multiple-Ascending Doses)

Procedure	Screening	Days										FU ^a	ED ^b	Comments
		-1	1	2	3 to 6	7	8	9 to 13	14	15 to 17	28			
Informed Consent	X													
Admission to CRU ^c		X												
Discharge from CRU											Day 17			
LY3478045 Administration						X								
Medical History	X													Information regarding occasional use of vitamin/mineral supplements will be taken as a part of the medical history evaluation at the time of subject screening.
Complete Physical Examination	X											X	X	Targeted PE may be conducted at other visits at the discretion of the investigator.
Height	X													
Weight	X	X									Day 15	X	X	
Pregnancy Test	X	X										X	X	Serum pregnancy test will be performed at screening and urine pregnancy test will be performed at all other specified

	Screening	Days										FU ^a	ED ^b	Comments
Procedure	≤28 days before Day -1	-1	1	2	3 to 6	7	8	9 to 13	14	15 to 17	28			
														timepoints.
Blood Pressure and Pulse Rate (Supine) ^c	X	X	P, every 1 h up to 12 h postdose	24, 36 h	48, 72 h				X		X	X		
Body Temperature	X	X										X	X	
Clinical Laboratory Tests (See Appendix 2)	X	X	P		Day 4	X			X		X	X		
Serum Creatinine			X			X			X					
Total Testosterone, Follicle-Stimulating Hormone, and Luteinizing Hormone	X		P	P							X	X	Samples will be collected early in the morning on Days 1 and 2, at the same time for both days, before or immediately after breakfast.	
Single 12-Lead ECG	X										X	X		
TriPLICATE 12-Lead ECG			Predose: 1.5 h, 1 h, and 30 min.						P, 0.5, 1.5, 2.5, 4, 6, 8, 12, 16 h	24 h				
Adverse Event Recording	X	X	X	X	X	X	X	X	X	X	X	X		
Pharmacokinetic Sampling ^d			P, 0.75, 1.5, 3, 4, 6, 8, 12, 16 h	24 h (predose)		P			P, 0.75, 1.5, 3, 4, 6, 8, 12, 16 h	24, 48, 72 h			Sampling times may be adjusted based upon review of interim PK	
Fasting Insulin and Adiponectin			P						P					
Meal (Low Fructose)			20 min, 6 h, 12 h						20 min, 6 h, 12 h					

Procedure	Screening ≤28 days before Day -1	Days										FU ^a	ED ^b	Comments
		-1	1	2	3 to 6	7	8	9 to 13	14	15 to 17	28			
Fructose Beverage (for Fructose Tolerance Test)			during meal: 20 min, 6, 12 h						during meal: 20 min, 6, 12 h					
Fructose Tolerance Test Assay ^d			CCI	CCI					CCI	CCI				
Genetic Sample		P												
Fasting Biomarker Samples (Nonpharmacogenetic)		X		X							Day 15			

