7.1. Treatment Administered

LY3478045 or placebo will be administered orally with approximately 240 mL of room temperature water in the morning of each dosing day (Day 1 in SAD; Days 1 to 14 in MAD) in a sitting position. Subjects will not be allowed to lie supine for 2 hours after dosing, unless clinically indicated or for study procedures.

Table GZKA.3. Treatments Administered

Treatment Name	LY3478045	Placebo	Atorvastatin
Dosage Formulation	CC1	Capsules	Tablets
Dose strength		-	40 mg
Route of Administration	Oral	Oral	Oral

The investigator or designee is responsible for

- explaining the correct use of the investigational product(s) to the site personnel
- verifying that instructions are followed properly
- maintaining accurate records of investigational product dispensing and collection, and
- returning all unused medications to Lilly or its designee at the end of the study

Note: In some cases, sites may destroy the material if, during the investigative site selection, the evaluator has verified and documented that the site has appropriate facilities and written procedures to dispose off the clinical materials.

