8.2. Discontinuation from the Study

Subjects will be discontinued under the following circumstances:

- Enrollment in any other clinical study involving an investigational product or enrollment in any other type of medical research judged not to be scientifically or medically compatible with this study
- Participation in the study needs to be stopped for medical, safety, regulatory, or other reasons consistent with applicable laws, regulations, and good clinical practice (GCP)
 - Any TEAE or SAE considered possibly or probably related to study drug that is severe or medically significant but not immediately life threatening; or where hospitalization or prolongation of hospitalization is indicated; or is disabling; or limits self-care activities of daily living.
 - Any TEAE or SAE regardless of attribution to study drug that has life-threatening consequences or urgent intervention is indicated.
- Investigator Decision

- the investigator decides that the subject should be discontinued from the study
- if the subject, for any reason, requires treatment with another therapeutic agent that has been demonstrated to be effective for treatment of the study indication, discontinuation from the study occurs prior to introduction of the new agent
- Subject Decision
 - the subject, or legal representative, requests to be withdrawn from the study.

The replacement strategy for discontinued participants is described in Section 10.1. If deemed appropriate by the investigator, early discontinuation procedures will be performed as shown in the Schedule of Activities (Section 2).

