9.2. Adverse Events

Investigators are responsible for monitoring the safety of subjects who have entered this study and for alerting Lilly or its designee to any event that seems unusual, even if this event may be considered an unanticipated benefit to the subject.

The investigator is responsible for the appropriate medical care of subjects during the study.

Investigators must document their review of each laboratory safety report.

The investigator remains responsible for following, through an appropriate health care option, AEs that are serious or otherwise medically important, considered related to the investigational product or the study, or that caused the subject to discontinue the investigational product before completing the study. The subject should be followed up until the event resolves, stabilizes with appropriate diagnostic evaluation, or is reasonably explained. The frequency of follow-up evaluations of the AE is left to the discretion of the investigator.

The investigator will record all relevant AE and SAE information in the eCRF. After the informed consent form (ICF) is signed, study site personnel will record, via eCRF, the occurrence and nature of each subject's preexisting conditions, including clinically significant signs and symptoms of the disease under treatment in the study. Additionally, site personnel will record any change in the condition(s) and the occurrence and nature of any AEs.

The investigator will interpret and document whether an AE has a reasonable possibility of being related to study treatment, or a study procedure, considering the disease, concomitant treatment or pathologies.

Safety data, in particular AEs, SAEs, and adverse laboratory abnormalities, will be independently assessed by the investigator, and will be considered related to the investigational product unless there is clear evidence that the event is not related.

Planned surgeries should not be reported as AEs unless the underlying medical condition has worsened during the study.

If a subject's investigational product is discontinued because of an AE, study site personnel must report this to Lilly or its designee via eCRF.

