9.4.5.1. Hepatic Safety

If a study participant experiences elevated ALT $\geq 3x$ ULN, AST $\geq 3x$ ULN, ALP $\geq 2x$ ULN, or TBL $\geq 2x$, tests specified in [Appendix 4](#) should be repeated within 48 to 72 hours to confirm the abnormality and to determine if the abnormality is increasing or decreasing.

If the abnormality persists or worsens, clinical and laboratory monitoring, and evaluation for possible causes of abnormal liver tests should be initiated by the investigator in consultation with the Lilly-designated medical monitor. At a minimum, this evaluation should include physical examination and a thorough medical history, including symptoms, recent illnesses (e.g., heart failure, systemic infection, hypotension, or seizures), recent travel, history of concomitant

medications (including over-the-counter), herbal and dietary supplements, history of alcohol consumption and other substance abuse.

Initially, monitoring of symptoms and hepatic biochemical tests should be done at a frequency of 1 to 3 times weekly, based on the participant's clinical condition and hepatic biochemical tests. Subsequently, the frequency of monitoring may be lowered to once every 1 to 2 weeks, if the participant's clinical condition and laboratory results stabilize. Monitoring of ALT, AST, ALP, and TBL should continue until levels normalize or return to approximate baseline levels.

Additional hepatic safety data collection (hepatic safety CRF) should be performed in study participants who meet 1 or more of the following 5 conditions:

- Elevation of serum ALT to ≥ 5 x ULN on 2 or more consecutive blood tests
- Elevated TBL to ≥ 2 x ULN (if baseline TBL < 1.5 x ULN) (except for cases of known Gilbert's syndrome)
- Elevation of serum ALP to ≥ 2 x ULN on 2 or more consecutive blood tests
- Hepatic event considered to be an SAE
- Discontinuation of study drug due to a hepatic event

Note: The interval between the 2 consecutive blood tests should be at least 2 days.

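### In Protocol Section 8.1 the ALT/AST >5 x ULN duration condition cannot be met, while a dose remains, by a rise that starts after the first Part B dose

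*Protocol*

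**What the plan says.** Section 8.1 applies to Part B only and is advisory: the investigator considers stopping the product after consulting the medical monitor. Four of its conditions use ALT or AST.

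- Two rest on the transaminase alone: a value above 8 x ULN, with no duration attached, and "ALT or AST >5X ULN sustained for more than 2 weeks or".
- Two start at 3 x ULN but need a second finding. One is "ALT or AST >3X ULN and TBL >2X ULN or international normalized ratio >1.5 or"; the other requires symptoms, fever, rash or eosinophilia.

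The remaining conditions concern alkaline phosphatase and creatine kinase. Section 7.1 gives the dosing days as "Day 1 in SAD; Days 1 to 14 in MAD".

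Other sections also bear on a liver-test rise:

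- **Section 9.4.5.1:** from 3 x ULN, tests "should be repeated within 48 to 72 hours to confirm the abnormality". If the abnormality persists or worsens, monitoring and evaluation "should be initiated by the investigator in consultation with the Lilly-designated medical monitor". It also calls for hepatic CRF data when ALT is at or above 5 x ULN on two or more consecutive tests at least 2 days apart.
- **Section 9.2:** adverse laboratory abnormalities "will be considered related to the investigational product unless there is clear evidence that the event is not related".
- **Section 8.2:** a subject is discontinued for a related event that is "severe or medically significant but not immediately life threatening", and separately whenever the investigator so decides.

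**The concern.** A condition for stopping a drug is useful only if it can be met while there is still drug to stop. The duration in this line is longer than the interval between the first and last Part B dose. A reader of Section 8.1 could believe that an isolated transaminase rise above 5 x ULN has its own stopping prompt during dosing. For a rise caused by the study drug it has none until the value passes 8 x ULN. This is a first-in-human study with no expected benefit to the subjects, so each line of the stopping list ought to be able to operate.

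**Working it through.** **Inputs**

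- First dose Day 1, last dose Day 14 (Sections 5.1.2 and 7.1). The documents describe no dosing after Day 14.
- Duration required: more than 14 days, first met at 15 whole days (Section 8.1).
- The day columns in Section 2.3 run from Day -1 to Day 1, so there is no Day 0.
- Scheduled safety laboratory tests in Part B: Day -1 (Cohorts 1 and 3) or Day -3 (Cohorts 2 and 4), Day 1 predose, Day 4, Day 7, Day 14 and follow-up on Day 28. These come from Sections 2.2 and 2.3, whose table layout is damaged in the available text. The first result below does not depend on them.

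**Rise starting after the first dose**

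Duration at the last dose = 14 − onset day.

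| Onset or first detection | Duration at Day 14 | Day on which 15 days is reached | Days after last dose |
|---|---|---|---|
| Day 1 | 14 − 1 = 13 | 1 + 15 = Day 16 | 2 |
| Day 4 | 14 − 4 = 10 | 4 + 15 = Day 19 | 5 |
| Day 7 | 14 − 7 = 7 | 7 + 15 = Day 22 | 8 |

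The longest possible duration is 13 days against a requirement of more than 14. Counting in hours instead of whole days does not change this.

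**Rise already present before the first dose**

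With no Day 0, the time from Day −a to Day b is a + b − 1 days.

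- Day -3 to Day 13: 3 + 13 − 1 = 15 days. Met on Day 13.
- Day -2 to Day 14: 2 + 14 − 1 = 15 days. Met on Day 14. No scheduled test falls on Day -2, and the next one is Day 1 predose, so the schedule alone would not document it.
- Day -1 to Day 14: 1 + 14 − 1 = 14 days. Not met.

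The Day -3 and Day -2 cases arise in Cohorts 2 and 4, which are admitted on Day -3. They should be uncommon, because Section 6.2 excludes ALT or AST above 1.5 x ULN. They are not ruled out: screening may be up to 28 days earlier, and Section 6 lets subjects continue despite laboratory abnormalities on Day -3 unless the investigator or sponsor says otherwise.

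**What is left in the list**

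Of the four ALT/AST conditions, two need a second finding. Of the two that do not, one cannot act on a treatment-emergent rise. The one that remains is >8 x ULN.

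**Effect of a confirmed >5 x ULN condition**

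Assume that the dose on the day of the repeat is given and that the result is known before the next morning's dose. Doses left = 14 − confirmation day.

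| First found | Repeat at 48 to 72 h | Doses left |
|---|---|---|
| Day 4 | Day 6 or 7 | 14 − 6 = 8 or 14 − 7 = 7 |
| Day 7 | Day 9 or 10 | 14 − 9 = 5 or 14 − 10 = 4 |
| Day 14 | Day 16 or 17 | none |

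**The case against.** The strongest reply is that the line's purpose is already served elsewhere. Section 8.1 compels nothing; it asks the investigator to consider stopping after consulting the monitor. Section 9.4.5.1 brings any persisting or worsening rise from 3 x ULN to the same two parties, and a repeated ALT at or above 5 x ULN triggers extra data collection during dosing. Under Section 9.2 such a rise is presumed related, so Section 8.2 discontinues the subject if it is judged severe or medically significant, and the investigator may discontinue on judgement alone. Section 7.4.1 can also interrupt dosing when a subject on active drug has two clinically significant events, which may include laboratory findings. An inert line neither permits continued dosing nor blocks any of these routes.

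Most of this stands, and it sets the size of the point. It does not make the line operable. Neither Section 9.4.5.1 nor Section 8.2 sets a transaminase level at which stopping is to be considered, and the 5 x ULN data-collection trigger covers ALT only and is not a stopping prompt.

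A reader might infer that subjects with values between 5 and 8 x ULN would be dosed without attention, or that >8 x ULN is the only way to stop the drug for a liver signal. The documents do not support either reading, for the reasons just given and because of the two combined conditions from 3 x ULN. A reader might also infer that the line can never be met. That goes too far as well: a rise that predates dosing could meet it on Day 13 or 14.

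It is also fair to say that the replacement is stricter than the present text and that no document supports its exact threshold. That is why the threshold is left for the sponsor's medical staff to confirm.

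**Conclusion.** The point holds as a minor wording defect. The core result needs only the dosing days and the stated duration. The statement about >8 x ULN is limited to the conditions in Section 8.1 that rest on ALT or AST alone. What lacks a listed stopping prompt during dosing is narrow: a treatment-emergent ALT or AST above 5 and up to 8 x ULN, with none of the additional findings in the combined conditions and not judged severe or medically significant. Even that case reaches the medical monitor if it persists or worsens. No endpoint, analysis or escalation rule is affected. The result assumes dosing as planned on Days 1 to 14.

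**What to change.** Keep the list advisory and replace the line with one that can be met within 14 days of dosing, for example: *ALT or AST >5X ULN confirmed on the 48 to 72 hour repeat test*. The sponsor's medical staff should confirm the threshold, since this is stricter than the current text. It fits the attention that Section 9.4.5.1 already gives to repeated ALT at or above 5 x ULN.

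The cost is one line of protocol wording. The repeat test is already required from 3 x ULN, so no visit or scheduled sample is added. The downside is that a few more subjects may be considered for stopping.

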8.2. Discontinuation from the Study

Subjects will be discontinued under the following circumstances:

- Enrollment in any other clinical study involving an investigational product or enrollment in any other type of medical research judged not to be scientifically or medically compatible with this study
- Participation in the study needs to be stopped for medical, safety, regulatory, or other reasons consistent with applicable laws, regulations, and good clinical practice (GCP)
 - Any TEAE or SAE considered possibly or probably related to study drug that is severe or medically significant but not immediately life threatening; or where hospitalization or prolongation of hospitalization is indicated; or is disabling; or limits self-care activities of daily living.
 - Any TEAE or SAE regardless of attribution to study drug that has life-threatening consequences or urgent intervention is indicated.
- Investigator Decision

- the investigator decides that the subject should be discontinued from the study
- if the subject, for any reason, requires treatment with another therapeutic agent that has been demonstrated to be effective for treatment of the study indication, discontinuation from the study occurs prior to introduction of the new agent
- Subject Decision
 - the subject, or legal representative, requests to be withdrawn from the study.

The replacement strategy for discontinued participants is described in Section 10.1. If deemed appropriate by the investigator, early discontinuation procedures will be performed as shown in the Schedule of Activities (Section 2).

8.3. Subjects Lost to Follow-up

A subject will be considered lost to follow-up if he or she repeatedly fails to return for scheduled visits and is unable to be contacted by the study site. Site personnel are expected to make diligent attempts to contact subjects who fail to return for a scheduled visit or were otherwise unable to be followed up by the site.

8.4. Discontinuation of the Study

The study will be discontinued if Lilly or its designee judges it necessary for medical, safety, regulatory, or other reasons consistent with applicable laws, regulations, and GCP.

A safety investigation will be triggered to determine if the study should be terminated early based on the following criteria:

- Three study participants develop the same TEAE or SAE considered possibly or probably related to study drug that is severe or medically significant, but not immediately life threatening; or where hospitalization or prolongation of hospitalization is indicated; or is disabling; or limits self-care activities of daily living OR
- Two study participants develop any TEAE or SAE regardless of attribution to study drug that has life-threatening consequences or requires urgent intervention OR
- Death of any study participant at any time related to AE.

9. Study Assessments and Procedures

Section 2 lists the Schedule of Activities, detailing the study procedures and their timing (including tolerance limits for timing).

Appendix 2 lists the laboratory tests that will be performed for this study.

Appendix 5 provides a summary of the maximum number and volume of invasive samples, for all sampling, during the study.

Unless otherwise stated in the subsequent subsections, all samples collected for specified laboratory tests will be destroyed within 60 days of receipt of confirmed test results. Certain samples may be retained for a longer period, if necessary, to comply with applicable laws, regulations, or laboratory certification standards.

The specifications in this protocol for the timings of safety, PK, and PD sampling are given as targets to be achieved within reasonable limits. Modifications may be made to the time points based upon the safety and PK information obtained. The scheduled time points may be subject to minor alterations; however, the actual time must be correctly recorded in the electronic case report form (eCRF). Failure to obtain samples due to clinical issues, such as problems with venous access, technical difficulty with obtaining samples, or if the subject does not show up for planned procedural visits will not be considered a protocol deviation. However, the CRU will still be required to notify the sponsor in writing to account for missing samples to facilitate data reconciliation.

If the predicted mean exposure for the dose at any cohort is estimated to be higher than 71.7 $\mu\text{g}\cdot\text{hr}/\text{mL}$, only female subjects will be included in the cohort and mandated to stay in the CRU until 24 hours after the last dose.

